V2.0	CR	1 st May 2021	Revisions required by NIHR Additions: internal pilot feasibility study, COVID related questions, new voucher security supplier
V3.0	CR	5 th May 2021	Revised for QMERC
V4.0	CR	12 th August 2021	Main study removed Revised to only include pilot study

Contents

1. Glossary	
2. Signature page	
3. Summary and synopsis	
4. Introduction: the problem to be addressed	

Primary registry and	ISRCTN registry. Registration number tbc
trial number	
Countries of	England
recruitment	
Research Sites	(1) Doncaster Metropolitan Borough Council
	(2) Bradford Metropolitan Borough Council
	(3) London Borough of Tower Hamlets Council
	To undertake a pilot study in order to inform the design
	and conduct of a main trial to evaluate the impact of the
Aims	intervention on a range of interconnected challenges for
-	UK public health nutrition in areas of high deprivation
	and low fruit and vegetable consumption.
	Fresh Street a weekly voucher scheme for fresh FV with
	vegetable-based recipes, brief nutritional information &
	healthy eating and health-related behaviour change
Intervention	information delivered to all households in an area; all
	households are eligible, regardless of size, type or
	income. Vouchers are redeemable with local
	independent FV retailers.
Inclusion criteria	High deprivation (IMD deciles 1-4)
(clusters)	Below average FV consumption
· · · ·	
Methodology/ Study	Pilot RCT with process evaluation.
design Number of clusters/	Target - 22 clusters (est 600 households)
Target sample size	raiger - 22 clusiers (est our nousenous)
Primary outcome	Portions of FV eaten yesterday
Key secondary	Diet Quality, Food Insecurity, Long term health
outcomes	conditions
Process evaluation	To provide insight into the process of implementing the
	intervention, mechanisms of action of the intervention,
	and contextual factors which might impact the
	intervention.
Proposed Start and	1 st October 2021 - 1 st June 2022
•	
Date	

4. Introduction: the problem to be addressed

4.1. Unhealthy diets and food systems

This study addresses an issue of major strategic public health importance – how to create and enable sustainable and healthy diets, eating behaviours and food systems in areas of high deprivation. Current UK dietary patterns are suboptimal for health. As a nation, we are failing to meet the recommendations for healthy eating, with areas of high socio-economic deprivation being most at risk of suboptimal diets, food deserts and food insecurity (Bates, 2016).

Many communities in the UK are experiencing food insecurity, i.e. "the inability to afford, or have access to, food to make up a healthy diet" (Department of Health 2005), and consuming diets high in processed foods and low in fresh fruit and vegetables (FV). People living on low incomes are more likely to have a higher consumption of sugar and saturated fatty acids, and lower intake of fruit and vegetables and dietary fibre than recommended (Food Standards Agency, 2007).

Although the UK population is aware of the importance of FV for health, many people lack the means to ensure that their daily diets include sufficient FV. There are multiple reasons as to why this is the case: food deserts, heavy and pervasive 'cradle to grave' advertising for unhealthy food products, and poverty (FV is less affordable and comparatively less value for money when the priority is filling up, palatability, convenience and avoiding waste). This leads to sub-optimal FV consumption and increased preventable morbidity and mortality, substantial associated costs to society, and one of the most obese populations in Europe.

Local food systems are complex; incorporating elements of local, national and international companies, which produce and retail groceries and ready-to-eat foods. Interventions are needed to help reorient local food systems so that they support healthy eating patterns, advance health goals and advance important economic, social and environmental goals, which impact on health in the longer term (Parsons & Hawkes 2018).

Diet-related ill health in the UK costs the National Health Service (NHS) at least £6 billion annually and is responsible for about 10% of deaths and illness (Scarborough 2011). Furthermore, the burden of disease is higher in socioeconomically disadvantaged communities. There is, therefore, an urgent need to identify effective and cost-effective interventions to minimise poor diet, by increasing the intake of healthy food and reducing the intake of sugar-sweetened beverages and foods high in salt, sugar, and saturated fats. Optimal diet means substantial increases in FV, pulses, nuts, seeds, fish, seafood, olive oil, and omega-3. The UK 5 A Day guidelines state that adults should eat at least five 80g portions of a variety of FV every day. These national guidelines are based on WHO recommendations that consuming 400g of FV a day can reduce risks of chronic diseases, including heart disease, stroke, and some cancers (Hartley et al. 2013).

4.2. Cash transfer/ Voucher schemes

There is mounting evidence that price discounts are effective in increasing healthy food purchasing (An et al, 2013) and increasing consumption of healthier foods (Brambila-Macias et al, 2011). There is evidence that opening new independent FV retail outlets (farmers markets, produce stands, mobile produce markets), increases FV consumption in the short-term (Woodruff et al, 2018), including in food deserts. There are a number of established targeted voucher (cash transfer) programmes. In the USA, two programmes target those on low incomes: (i) The Supplemental Nutritional Assistance Programme (SNAP) is used to buy a wide range of products in supermarkets (the SNAP value is doubled if vouchers are used in farmers markets), and (ii) the Women Infant and Children (WIC) programme for those on low income.

In the UK, the Department of Health & Social Care funded 'Healthy Start' programme provides vouchers worth £4.25 per week, for FV, pulses, milk and infant formula to pregnant women and carers of children under four, and £8.50 for children under 1year, in households on income support (Healthy Start). Application is via healthcare providers, and vouchers are sent monthly. There was initial observational data which indicated that 'Healthy Start' was effective in increasing FV uptake (McFadden, 2014). However, most vouchers for children under 1 year are used for infant formula rather than FV (Crawley, 2018), the targeted nature of the scheme brings about stigma (McFadden, 2014) and uptake of the scheme is declining. In 2019 just 54.2% of eligible families were using the scheme (Department of Health, 2019).

4.3. Development and feasibility of the intervention

'Fresh Street' is an innovative multi-component intervention, which combines supplier specific vouchers for fresh FV with a range of diet and health information. The vouchers are offered to **all households** in a geographical area regardless of household type, size or income. The combination of fiscal measures with regular multi-faceted communication/ marketing information has been developed to reduce food insecurity, increase daily consumption of fresh FV, and improve dietary quality, support healthy dietary habits, and increase exposure to healthy food prompts.

In 2017, CR & MB & stakeholders developed and feasibility tested the 'Fresh Street' intervention in an area of high deprivation in the north of England funded by MRC PHIND, with support from Barnsley Metropolitan Borough Council and the Alexandra Rose Charity.

The feasibility of the scheme was assessed in four streets using rapid ethnographic assessment (Manderson et al, 1992) and voucher redemption information. The 12 month scheme was popular and seen to be of benefit to local people and local traders. Most (84%, 80/95) eligible households joined the scheme and most (89%) vouchers were redeemed. Householders frequently reported that the scheme made them think more about what they were eating, and prompted them to buy and eat more FV. The local FV shop and market stalls reported new customers and that existing customers were buying more. People frequently talked (unasked) about their health and some reported that the scheme motivated them to lose weight (Relton et al, 2020).

In 2018, a second feasibility test was conducted in a block of 54 two-bedroom flats in a deprived area of Sheffield ([name]). This was situated in a food desert (i.e.

no local supply of fresh FV). Vouchers were redeemable at the four FV stalls in Sheffield Moor Market (3 miles away), or exchanged for a £5 bag of fresh vegetables and apples delivered to the flats each week. About 75% of eligible households joined the scheme and 70%+ of the vouchers issued were redeemed. Doorstep conversations revealed similar responses to the Barnsley scheme (the scheme made them think more about what they were eating, and prompted them to buy and eat more FV) and market stalls reported new customers. However, interest in the weekly delivered £5 vegetable bag was low with most preferring to choose their own FV from the market stalls.

4.4. Summary and implications for research

- Many communities in the UK are failing to meet the recommendations for healthy eating, with areas of high socio-economic deprivation being most at risk of suboptimal diets, food deserts and food insecurity.
- Although the UK population is aware of the importance of FV for health, many people lack the means to ensure that their daily diets include sufficient FV.
- Interventions are needed to help re-orientate local food systems so that they support healthy eating patterns, advance health goals and advance the economic, social and environmental goals, which impact on health in the longer term.
- There is preliminary evidence of the acceptability and deliverability of 'Fresh Street' intervention.
- Research is now needed to assess the impact of this intervention on FV consumption, diet, health and the wider environment.

5. Aim and objectives

We aim to undertake a pilot study (consisting of a pilot trial and a process evaluation) in order to inform the design and conduct of a main trial to evaluate the impact of the Fresh Street scheme on a broad range of interconnected challenges for UK public health nutrition in areas of high deprivation and low fruit and vegetable consumption.

The pilot study objectives are to:

- a. Deliver the intervention in different sites
- b. Assess uptake of the intervention and identify factors which may impact on intervention success
- c. Create a manual describing a potential new public health intervention (Fresh Street)
- d. Test, refine and optimise household survey data collection methods
- e. Demonstrate that baseline primary outcome measure responses are obtainable from at least 50% of households
- f. Conduct a process evaluation to assist interpretation of findings, and inform implementation of the intervention
- g. Refine the methods for the main trial and process evaluation
- h. Gain insight into the perspectives of key stakeholder groups (e.g. Directors of Public Health, Community, Retail)
- i. Obtain additional intervention funding required for the main trial.
- j. Collect outcome data from pilot sites, if required.

Research hypothesis

We hypothesise that together the different components of the intervention provide the conditions required to trigger the behaviour changes needed to increase FV consumption and improve diet quality.

6. Study design

6.1. Pilot study design

Parallel group, cluster randomised controlled pilot trial (RCT) with integrated process evaluation. Clusters (streets) are randomised to intervention or no intervention.

6.2. PICO summary for the pilot trial

Population: Areas with a high deprivation index (IMD deciles 1-4) and low fruit and vegetable consumption are eligible to participate in the pilot trial

Intervention: Provision of Fresh Street scheme

Comparison: No provision of Fresh Street scheme

Outcomes: PRIMARY: Portions of FV consumed yesterday; SECONDARY: diet quality, food insecurity, long-term health conditions, health-related quality of life, life satisfaction;; and healthcare utilisation.

6.3. Progression criteria

The following progression criteria will be assessed towards the end of the pilot study by and the NIHR and the independent project steering committee (PSC). They will consider the process data and decide whether it is feasible to proceed to a main trial. In order to evaluate the trial feasibility, the PSC will apply the following stop/ modify/ go progression criteria:

Green (continue):

- Demonstrated we can collect data on the primary outcome measure (i.e. >50% of both groups provide baseline data*)
- Secured intervention funding for at least 856 households for at least two years

Amber (decision required from funder on whether to continue to the main trial):

- Demonstrated we can collect data on the primary outcome measure (i.e. > 25% of both groups provide baseline data*)
- Secured intervention funding for at least 856 households for at least one year

Red (stop as not feasible):

- Not demonstrated we can collect data on the primary outcome measure (i.e. < 25% of both groups provide baseline data*)
- Not secured intervention funding for 856 households for at least one year

 * 50% of households in study streets provide information from at least one person in that household

7. Methods

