We aim to ensure that we obtain valid unbiased data (RoB 2 for cluster randomized trials) (see section 7.10). Surveys will only be valid if both the name of the street and the house number is provided. This will be the case for both paper and on-line surveys. If we receive two or more valid responses (paper or paper and online) from the same household, then we will consider the paper survey response as the primary response. If two or more valid online surveys are received then we will consider the first valid online response as primary if there is no paper response.

Questions in the paper and the online surveys will be exactly the same. Paper surveys will be branded for each site e.g. Tower Hamlets Food and Health Survey (see Appendix 1).

However, the online surveys come in three different formats and have the following names: "What do you eat?", "Do you have enough to eat?" and "Virus Health and Wellbeing checKer (V-HAWK)". (see Table 2)

These online surveys will be integrated into QMUL 'Healthy People, Healthy Places' online platform (https://qmul.citizenlab.co/en/).

		Online
Data item	Measure/ Source	survey
		name
Primary outcome data		
Portions of FV eaten yesterday	Active Lives Survey	What do you
	(two questions)	eat?
Secondary outcome data		
Diet Quality Score (in the past month)	Diet Quality	What do you
	Questionnaire (DQQ)	eat?
Food insecurity (in the previous 12 months)	Food Insecurity	Do you have
	Experience Scale	enough to
	(FIES)	eat?
Long term conditions (fatigue, pain,	Questions from the	Virus-Health
insomnia, anxiety, depression, diabetes,	Yorkshire Health Study	And
breathing problems, high blood pressure,	(YHS) Health	Wellbeing
heart disease, osteoarthritis, stroke, cancer,	Questionnaire	checKer (V-
long COVID, other)		HAWK)
Virus symptoms, COVID diagnosis		V-HAWK
Life satisfaction	YHS Health	V-HAWK
	Questionnaire	
Health Related Quality of Life	EQ-5D	V-HAWK
Healthcare utilisation (last 3 months)	YHS Health	V-HAWK
	Questionnaire	
Free text comments (diet and health)		What do you
		eat
		V-HAWK
Respondent and hous	sehold information	

Respondent Ethnicity, Age group, Gender, COVID vaccine status, Consent to contact. Household Composition Street name and house number

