7.14. Data analysis

Analysis of voucher distribution and redemption data will enable us to assess uptake of the intervention (objective b) including weekly spending patterns of each household - how many vouchers were spent, and when and where.

We will assess what proportion of households contacted provide valid baseline primary outcome measure responses (objective e).

Any analysis of outcome data will be by intention-to-treat. All clusters and households for whom an outcome is available will be analysed according to the group to which they were randomised. Households which cannot be linked to a street participating in the study will be excluded.

The primary outcome analysis will compare the mean difference between intervention and control in portions of FV eaten the day before. A mixed regression model will be used where an individual household outcome at follow-up is adjusted for baseline cluster (street) mean score and site, and within cluster correlation is allowed for.

There is likely to be some contamination relating to sharing of vouchers, sharing of information, supplier effects and household churn i.e. households moving into or out of the intervention/ control streets. Potential sources of contamination will be monitored throughout during qualitative interviews and analyses adjusted where possible.

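### The response rule in Section 6.3 gives no verdict when the arms fall either side of 25%, and its footnote does not define the rate as primary outcome data

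*Protocol*

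**What the plan says.** Section 6.3 gives three response tiers, each carrying the same footnote mark:

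- Green: "Demonstrated we can collect data on the primary outcome measure (i.e. >50% of both groups provide baseline data".
- Amber: "Demonstrated we can collect data on the primary outcome measure (i.e. > 25% of both groups provide baseline data".
- Red: "Not demonstrated we can collect data on the primary outcome measure (i.e. < 25% of both groups provide baseline data".

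The footnote to all three reads "50% of households in study streets provide information from at least one person in that household". The section says that the steering committee will apply these criteria, and it reserves a funder decision for Amber only.

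Three other places describe the same rate:

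- Objective e in Section 5: "Demonstrate that baseline primary outcome measure responses are obtainable from at least 50% of households". It is not split by arm.
- Section 7.14: "We will assess what proportion of households contacted provide valid baseline primary outcome measure responses (objective e").
- Section 7.9, on validity: "Surveys will only be valid if both the name of the street and the house number is provided".

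Section 7.9 also says that online surveys will be added if paper response is too low. They come in three formats, and Table 2 lists the fruit and vegetable questions under only one of them, *What do you eat?*.

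**The concern.** This rate is one of the two things that decide whether a main trial follows, so every possible result should lead to one tier and the rate should have one meaning. Neither holds.

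First, Red is not the opposite of Amber. The opposite of both arms above 25% is at least one arm at or below 25%, but Red asks for "< 25% of both groups provide baseline data". Results between the two have no tier, and the choice would be made after the data are seen.

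Second, the tiers ask whether the primary outcome can be collected, while the footnote counts a household that supplies any information. A household without a fruit and vegetable answer could then help to show that fruit and vegetable data are obtainable.

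**Working it through.** **Inputs.** The cuts and footnote are from Section 6.3. Section 7.5 gives 22 clusters and about 300 households per arm (about 600 in all), and Section 7.6 gives 1:1 allocation. The street ICC for response is not given; 0, 0.02 and 0.05 are assumed.

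**The plan's own figure.** Section 7.9 gives a maximum margin of error of 7% at 200. Check: 1.96 × √(0.5 × 0.5 / 200) = 6.93%. It reproduces, with households treated as independent. The progression cuts themselves are not derived from a calculation.

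**Step 1: apply the tiers literally.**

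| Arm rates | Both > 50% | Both > 25% | Both < 25% | Tier |
|---|---|---|---|---|
| 60% / 30% | no | yes | no | Amber |
| 50% / 50% | no | yes | no | Amber, although objective e is met |
| 30% / 20% | no | no | no | none |
| 60% / 20% | no | no | no | none |
| 55% / 24% | no | no | no | none |
| 25% / 25% | no | no | no | none |

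**Step 2: how often chance alone produces a split.** Take 11 streets of 27 households per arm (297, close to 300). With that number an arm cannot land on exactly 25%, since 0.25 × 297 = 74.25. If q is the chance that an arm falls below 25%, then P(no tier) = 2q(1 − q) when both arms have the same true rate. Simulated results, with a beta-binomial model by street:

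| True rate, both arms | ICC 0 | ICC 0.02 | ICC 0.05 |
|---|---|---|---|
| 25% | 0.50 | 0.50 | 0.50 |
| 28% | 0.23 | 0.30 | 0.36 |
| 30% | 0.06 | 0.12 | 0.19 |

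A hand check at 28% and ICC 0.05: design effect 1 + 26 × 0.05 = 2.3; standard error √(0.28 × 0.72 × 2.3 / 297) = 0.0395; z = (0.25 − 0.28) / 0.0395 = −0.76; q = 0.224; 2 × 0.224 × 0.776 = 0.35. This agrees with the simulation.

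**Step 3: the footnote against the bullets.** Suppose 330 of 600 households return something, spread evenly over the arms. All households are contacted, so the denominator is 600 either way.

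- Any information: 330 / 600 = 55.0%, above the Green cut.
- Valid primary outcome data in 90% of returns (assumed): 297 / 600 = 49.5%, so Amber.
- In 80% of returns (assumed): 264 / 600 = 44.0%, so Amber.
- In 100% of returns: 55.0%, with no difference.

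In this example Green is lost once the valid share is 300 / 330 = 90.9% or lower.

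**Step 4: where such returns could come from.** If online surveys are introduced, Table 2 places the primary outcome in *What do you eat?* only. A household returning only *Do you have enough to eat?* or V-HAWK gives information but no fruit and vegetable data. Online surveys are added when paper response is below 50%, which is when the Green cut is already in doubt.

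**The case against.** On the tiers, Red opens with the words for not having demonstrated collection, the negation of Amber's opening. Read that way, 30% v 20% fails Amber and is Red. The condition after the i.e. says otherwise, so the text still has to be reconciled. One could also pool the arms, since the footnote is not split by arm; the bullets, however, speak of both groups. Section 6.3 lets the funder and committee consider process data and decide, but it also says that the committee will apply these criteria, so discretion does not supply the missing tier. It is fair that the exposure is concentrated near 25% and falls to 6% to 19% at a true 30%.

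On the footnote, it may be meant only to fix the unit: one respondent per household is enough. Section 7.8 puts the primary questions at the start of the survey, so blank answers on paper may be few. Both points limit the size of the problem. They do not explain a footnote that states 50% under a 25% tier, or the online formats without the primary questions.

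Two stronger readings are tempting. A reader might infer that Sections 6.3 and 7.14 use materially different denominators, households in the streets against households contacted, and that the same data could move a full tier. The protocol does not support this: Section 7.9 plans to contact every household in both arms, with letterbox delivery where nobody answers, and Section 7.14 sets no tiers. A reader might also infer that a particular rule for combining the response and funding verdicts is required. Any such rule, for instance taking the worse of the two, would be a design choice and not a correction.

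**Conclusion.** The response rule is wrong as written, in two ways that can be corrected in the wording. Split results around 25%, and exactly 25%, have no tier. With about 300 households per arm the chance of this is about 50% at a true 25% in both arms and about 23% to 36% at 28%, assuming equal true rates, equal street sizes and a street ICC of 0 to 0.05. The footnote does not match the bullets it defines, in what it counts or in the percentage it states. Its effect on the rate depends on the share of returns without valid primary outcome data, which the protocol does not give; at an assumed 10% a 55% result becomes 49.5%. The mismatch between more than 50% in Section 6.3 and at least 50% in objective e is minor, and the same edit settles it.

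**What to change.** 1. Make the tiers exhaustive. Green: both arms at least 50%, matching objective e. Amber: both arms at least 25%, but not both at least 50%. Red: either arm below 25%.
2. Replace the footnote with one definition, used in Sections 5, 6.3 and 7.14. Numerator: households with a valid survey (street name and house number) and both the fruit and the vegetable question answered. Denominator: all eligible private residential households in the randomised streets. Report it by arm.
3. State in Section 7.14 that households contacted means this same set. This is a clarification only.

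No extra data are needed. The reported rate may be slightly less favourable, and the steering committee and funder would need to agree the wording, preferably before the baseline response rates are seen.
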